### **5.5.5. Dose Modifications**

Every effort should be made to administer the study treatments at the planned dose and schedule.

#### **5.5.5.1. Glasdegib or Placebo in Subjects Receiving Intensive Chemotherapy and Non-Intensive Chemotherapy**

In the event of Grade 3 or Grade 4 non-hematologic, study-treatment-related toxicity, dosing may be delayed and/or dose reduced. The glasdegib dose should be reduced 1 dose level at a time, in increments of 25 mg (75 mg QD, 50 mg QD, in the form of 3 or 2 x 25 mg tablets respectively).

Glasdegib or placebo does not need to be delayed or dose reduced for hematologic, study-treatment-related toxicity.

Glasdegib or placebo may be interrupted or permanently discontinued for any reason as per good clinical practice. Glasdegib or placebo should be permanently discontinued if interruptions are for more than 28 **consecutive** days when not required by the protocol (ie, HSCT period).

Dose escalations will not be allowed following glasdegib/placebo dose reductions.

Dose modifications may occur in three ways:

- **Within a cycle or within Induction 1, 2:** Dosing interruption until adequate recovery followed by dose reduction (if required) of glasdegib during a given treatment cycle.
- **Between cycles or between Induction 1, 2:** The next treatment cycle may be delayed if toxicity from the preceding cycle persists.
- **In the next cycle or within the next Induction:** Dose reduction may be required based on toxicities experienced in the previous cycle.

When chemotherapy is given, a Cycle is determined by chemotherapy administration schedule. A Cycle is 28 days, but will be extended if there are dose delays or modifications in the chemotherapy backbone. For Induction, there is no cycle and this therapy is referred to as Induction 1 and Induction 2.

When glasdegib or placebo is given alone, it is always in a 28 day Cycle.

No crossover between treatment arms will be permitted as crossover could significantly impact the primary endpoint of overall survival. Investigators are discouraged from prescribing glasdegib after discontinuation of study therapy.

#### **5.5.5.2. Dosing Interruptions for Glasdegib/placebo Non-hematological Toxicities**

Subjects experiencing Grade 3 or 4 non-hematological toxicities potentially attributable to glasdegib or placebo should have their glasdegib or placebo treatment interrupted regardless of when it occurs in the cycle until the toxicity resolves or returns to baseline or  $\leq$  Grade 1, as described in [Table 9](#).

If these parameters have not been met following >28 consecutive days of dose interruption, glasdegib or placebo should be permanently discontinued. If glasdegib or placebo treatment is permanently discontinued, patients may continue single-agent treatment with daunorubicin, cytarabine, or azacitidine, if according to the investigator's judgment a clinical benefit has been observed, and following discussion between the investigator and the sponsor.

**Table 9. Glasdegib or Placebo Dose Modifications for Non Hematologic Toxicities (Excluding QTc Prolongation, Muscle Spasms, and Myalgia)**

Toxicity (NCI CTCAE version 4.03)	Glasdegib or Placebo

≥ Grade 3 toxicity (Nausea, vomiting, and/or diarrhea must persist at ≥ Grade 3 (despite maximal appropriate medical therapy) to require dose modification).
	
Hold study drug until toxicity has recovered to baseline or ≤ Grade 1.
 
First episode: Decrease by 1 dose level.
 
Second episode: Decrease by 1 dose level.
 
Third episode: Permanently discontinue.

Potential DILI/Hy's Law (as defined in Section 8.4.2).
	
Interrupt glasdegib/placebo dosing. If an alternative cause is found, restarting of glasdegib/placebo at the same dose may be considered.

Confirmed DILI/Hy's Law (as defined in Section 8.4.2).
	
Glasdegib/placebo should be permanently discontinued.

Appropriate follow-up assessments should be implemented until adequate recovery (toxicity resolves or returns to baseline) occurs.

Depending on when the adverse event resolved, treatment interruption may lead to the patient missing all subsequent planned doses of glasdegib or placebo within the cycle. If the AE leading to treatment interruption recovers within the same cycle, re-commencement of dosing in that cycle is allowed. Glasdegib or placebo doses omitted for toxicity will not be replaced within that cycle (eg, cycles will not be prolonged beyond the 28 days in order to make up for any missed glasdegib or placebo doses during that cycle).

The need for a dose reduction at the time of treatment resumption should be based on the criteria outlined in Table 9, unless specifically agreed otherwise following discussion between the investigator and the sponsor. If a dose reduction for glasdegib or placebo is applied in the same cycle, the patient must return to the clinic to receive a new supply of drug.

In the event of glasdegib or placebo treatment interruption for reasons other than treatment-related toxicity (eg, elective surgery) for a duration >28 days, the details of treatment resumption will be determined in consultation with the sponsor. Glasdegib/placebo dose modifications for mean QTcF (mQTcF) prolongation are outlined in [Table 10](#).

**Table 10. Glasdegib Dose Modifications for mean QTcF (mQTcF) Prolongation**

CTCAE v 4.03	Grade 1	Grade 2	Grade 3**	Grade 4**	
Electrocardiogram QT corrected (QTc) interval prolonged*	450-480 msec	481-500 msec	≥501 msec on at least two separate ECGs	QTc ≥501 msec or >60 msec change from baseline and Torsade de pointes or polymorphic ventricular tachycardia or signs/symptoms of serious arrhythmia	

*The severity of QTc prolongation assessment is to be determined by calculating a mean QT of 3 consecutive ECGs performed approximately 2 minutes (but no longer than 5 minutes) apart using the Frederica correction method (mQTcF).
 
**Please see Section 8.4.1 for protocol specified SAE reporting requirement of Grade 3 or 4 mQTcF prolongation.
					
Category	Action	Grade			
		1	2	3	4
General management	Assess electrolyte levels and supplement as clinically indicated		X	X	X
	Review and adjust concomitant medications with known QTc interval-prolonging effects		X	X	X
ECG monitoring	Monitor ECGs at least weekly for 2 weeks following resolution of mQTcF prolongation to ≤480 msec		X	X	X
Initial glasdegib action	Discontinue and do not re-challenge				X
	Interrupt treatment			X	
	Continue treatment at same dose	X	X		
Resume glasdegib dosing	If no prior glasdegib dose interruption related to QTcF prolongation has occurred, resume at a reduced dose of 75 mg once daily when mQTcF interval returns to within 30 msec of baseline or ≤480 msec			X	
	If one prior glasdegib dose interruption related to QTcF prolongation has occurred, resume at a reduced dose of 50 mg once daily when mQTcF interval returns to within 30 msec of baseline or ≤480 msec			X	
Discontinue glasdegib permanently	If two prior glasdegib dose interruptions related to QTcF prolongation have occurred			X	

QTc criteria for dose modifications does not apply to subjects with a functioning pacemaker, whether the rhythm is paced or not. Dose modifications for glasdegib/placebo in case of drug class related AEs (muscle spasms, myalgia) are outlined in [Table 11](#).

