**Table 11. Dose Modifications for glasdegib/placebo in Case of Drug Class Related AEs**

Muscle Spasms or Myalgia	Grade 1	Grade 2	Grade 3
Glasdegib/ Placebo	
Continue at same dose level.
 
Administer oral rehydration solutions containing electrolytes.a
 
Consider other appropriate interventions (eg, anti-spasmodics) as per institutional guidelines.
 
Evaluate levels of: CK, Vit B6, Vit D, ferritin, transferin and electrolytes (Na, K, Mg, Ca and P).b
 
If CK is elevated, evaluate urine and serum myoglobin, CK isoenzymes, and plasma creatinine.
	
Continue at same dose level.
 
Administer oral re-hydration salts containing electrolytes.a
 
Consider other appropriate interventions (eg, anti-spasmodics) as per institutional guidelines.
 
Evaluate levels of: CK, Vit B6, Vit D, ferritin, transferin and electrolytes (Na, K, Mg, Ca and P).b
 
If CK is elevated, evaluate urine and serum myoglobin, CK isoenzymes, and plasma creatinine.
 
If event persists, hold dose until resolution to Grade ≤1.
 
Upon resolution, restart at prior dose, or for prolonged muscle spasms, consider reducing dose by one dose level.
	
Hold dose.
 
Administer oral re-hydration salts containing electrolytes.a
 
Consider other appropriate interventions (eg, anti-spasmodics) as per institutional guidelines.
 
Evaluate levels of: CK, Vit B6, Vit D, ferritin, transferin and electrolytes (Na, K, Mg, Ca and P).b
 
If CK is elevated, evaluate urine and serum myoglobin, CK isoenzymes, and plasma creatinine.
 
Upon resolution to Grade ≤1, restart study treatment at next lower dose level.
 
If the event does not resolve within 3 weeks to Grade ≤1, at the discretion of the Investigator the dose may be restarted at the next lower dose level or the subject may be permanently discontinued from study treatment.

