
Abbreviations: CK creatinine kinase; Vit vitamin; Na sodium; K potassium; Mg magnesium; Ca calcium; P phosphorous.
 
a. Electrolyte replacement drinks should include Na, K, Mg, Ca and P. Consideration should be given to ensuring adequate hydration prior to bedtime, and whenever fluid intake is decreased for a prolonged duration.
 
b. Labs may be drawn as unscheduled assessments between protocol visits.
 
In the event of alopecia or dysgeusia, investigator discretion should be applied with respect to dose interruption and/or dose reduction of glasdegib/placebo as preliminary analysis of available clinical data suggests that these events are not dose dependent.
			

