### **5.8.1. Restricted or Prohibited Concomitant Medications**

The following medications are not allowed during the active study treatment period:

- Agents used to treat AML;
- Investigational agents;
- Concurrent administration of herbal preparations;
- CYP3A4/5 Inducers: A drug-drug interaction study in health subjects with the strong CYP3A4 inducer, rifampin, resulted in a 70% decrease in plasma exposures ( $AUC_{inf}$ ) and a 35% decrease in peak plasma concentration ( $C_{max}$ ) of a single 100-mg oral dose of glasdegib. Therefore co-administration of glasdegib and moderate/strong CYP3A4/5 inducers is not permitted. A comprehensive list of moderate/strong CYP3A4/5 inducers is provided in [Appendix 5](#). However, if you are uncertain whether a concomitant medication is contraindicated, you should contact the Sponsor study team.

The following medications have use restrictions during the active study treatment period:

- CYP3A4/5 Inhibitors: In a healthy volunteer study, ketoconazole, a potent CYP3A4/5 inhibitor, produced a 2.4-fold increase in plasma exposure and a 1.4-fold increase in peak plasma concentration of glasdegib. Therefore a potential exists for drug-drug interactions with CYP3A4/5 inhibitors, and co-administration of glasdegib/placebo in combination with moderate/strong CYP3A4/5 inhibitors is not recommended. Selection of concomitant medication with no or minimal CYP3A4/5 inhibition potential is recommended. Moderate/strong CYP3A4/5 inhibitors ([Appendix 6](#) and [Appendix 7](#)) should be used with caution and only if considered medically necessary. If a moderate/strong CYP3A4/5 inhibitor is to be initiated in addition to glasdegib/placebo, the guidance provided in [Section 7.1.7](#) and dose modifications for QT prolongation per [Table 10](#) must be followed. If you

are uncertain whether a concomitant medication is a CYP3A4 inhibitor, you should contact the Sponsor study team.

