- Drugs with a known risk of Torsade de pointes (TdP): Glasdegib has been shown to have the potential to prolong the QTc interval in pre-clinical studies. In the first-in-subject study as single agent, Grade 3 QTcF prolongation was observed at the highest doses tested (400 mg and 600 mg). While the glasdegib dose evaluated in this study is 100 mg, the concomitant administration of glasdegib and drugs with a known risk of Torsade de pointes should be avoided whenever possible. A list of such drugs is provided in [Appendix 8](#). Use of these drugs is not recommended unless there are no alternatives. If a TdP drug is to be initiated in addition to glasdegib/placebo the guidance provided in [Section 7.1.7](#) and dose modifications for QT prolongation per [Table 10](#) must be followed.
- QT prolonging medications (without a risk of TdP) should be avoided whenever possible.
- Concomitant administration of multiple moderate/strong CYP3A4/5 inhibitors, TdP drugs, and/or QT prolonging medications (without a risk of TdP) is not recommended.

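### Table 10's fixed 75 mg resumption dose has no condition on current dose, so for a subject already at 50 mg it literally instructs an escalation that Section 5.5.5.1 bans

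*Protocol*

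**What the plan says.** Section 5.5.1.1 starts every subject at 100 mg daily. Section 5.5.5.1 sets the ladder below that: the dose is "reduced 1 dose level at a time, in increments of 25 mg (75 mg QD, 50 mg QD". No lower level is listed. The same section then says, without exception: "Dose escalations will not be allowed following glasdegib/placebo dose reductions". It also allows glasdegib or placebo to be interrupted or stopped for any reason under good clinical practice.

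Two tables in Section 5.5.5.2 move subjects down this ladder for toxicity other than QTc prolongation:

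- Table 9 covers non-hematologic toxicity of Grade 3 or higher. The first and second episodes each carry the instruction "Decrease by 1 dose level"; the third means permanent discontinuation. Its title excludes QTc prolongation.
- Table 11 covers muscle spasms and myalgia. After Grade 3, once resolved, the site is to "restart study treatment at next lower dose level". A note adds that for alopecia or dysgeusia "investigator discretion should be applied with respect to dose interruption and/or dose reduction of glasdegib/placebo".

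Table 10 covers QTcF prolongation and works differently. After a Grade 3 event, if no earlier interruption "related to QTcF prolongation has occurred, resume at a reduced dose of 75 mg once daily". With one earlier QTcF interruption the dose is 50 mg. With two, the drug is stopped. Grade 4 means stopping without rechallenge.

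Other sections send sites to Table 10. Section 5.8.1 says, for moderate or strong CYP3A4/5 inhibitors, that "dose modifications for QT prolongation per [Table 10](#) must be followed". It gives the same instruction for drugs with known torsade risk, in the sentence that begins "If a TdP drug is to be initiated in addition to glasdegib/placebo the guidance provided in". Section 7.1.7 refers any subject with a mean QTcF above 480 msec to the table.

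**The concern.** Tables 9 and 11 use relative steps, which can only lower the dose. Table 10 uses fixed milligram amounts keyed to a count of QTcF interruptions. A fixed amount is safe only if every subject reaching that row is at or above it, and nothing in the protocol guarantees this for the 75 mg row.

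The error would arise at a sensitive moment. Section 8.4.1 makes Grade 3 QTcF prolongation a reportable SAE whatever the cause or arm. A site following the table literally would restart the subject on more drug than the subject was taking when the event occurred. A site following Section 5.5.5.1 would have to depart from the table. What is at stake is dosing safety, and consistency between sites, in a small number of subjects.

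**Working it through.** No sample size, power or alpha figure is involved. The check traces one sequence through the rules and then compares each Table 10 dose with each dose a subject could be taking.

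**Can the state be reached?**

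1. Start: 100 mg (Section 5.5.1.1).
2. First Table 9 episode: 100 − 25 = 75 mg.
3. Second Table 9 episode: 75 − 25 = 50 mg. A Table 11 reduction, or a discretionary one for alopecia or dysgeusia, could replace either step.
4. First Grade 3 QTcF event, with no earlier QTcF interruption. Table 9 excludes QTc prolongation, so this does not count as its third episode and does not trigger its stopping rule. Table 10 governs.
5. Table 10, row for no earlier interruption: resume at 75 mg.

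Change from current dose: 75 − 50 = +25 mg, or 25/50 = +50%. Against the starting dose: (75 − 100)/100 = −25%. So 75 mg is a reduction from the starting dose but an increase for this subject.

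**Does any other entry point upward?** Table 10 dose minus dose at interruption:

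| Dose at interruption | No earlier QTcF interruption (75 mg) | One earlier (50 mg) |
|---|---|---|
| 100 mg | −25 | −50 |
| 75 mg | 0 | −25 |
| 50 mg | **+25** | 0 |

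Only one entry is positive. The 50 mg row cannot produce an increase, because 50 mg is the lowest listed level. These are table entries, not subject frequencies, and say nothing about how often the state occurs.

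**What do the rules imply when read together?**

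- Table 10 says to resume after a first Grade 3 event. It requires stopping only for Grade 4, or for Grade 3 after two earlier QTcF interruptions.
- Section 5.5.5.1 forbids going above 50 mg.
- The ladder lists nothing below 50 mg.

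The only listed dose that satisfies all three is 50 mg. A careful reader can reach this, but it has to be assembled from separate provisions, and the row sites are sent to names a different dose.

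**Does another clause give the dose directly?** The sponsor-agreement clause after Table 9 concerns the Table 9 criteria. The general discretion in Section 5.5.5.1 covers interruption and discontinuation but names no resumption dose. Section 7.1.7 refers back to Table 10.

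**The case against.** The strongest reply is that this is hardly a conflict. The row calls 75 mg a reduced dose, so it can be read as addressing subjects above 75 mg. The ban is unconditional, and 50 mg follows. Much of this stands: it is why actual escalation is unlikely, and why 50 mg can be taken as the implied dose. It does not repair the row. The row sets no dose condition, and the same table applies the word reduced to doses equal to the current one (75 mg for a subject on 75 mg, 50 mg for one on 50 mg), so the word cannot be relied on to exclude the subject on 50 mg.

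Safeguards also count. Resumption requires the mean QTcF to return to within 30 msec of baseline or to 480 msec or less. ECGs continue at least weekly for two weeks after resolution to 480 msec or less. The investigator may stop the drug, and Section 4.6 gives sites a route to the sponsor's medical staff. The exposure evidence is partly reassuring: Section 5.8.1 reports Grade 3 prolongation at the highest single-agent doses tested, 400 and 600 mg, and Section 1.2.4.1 reports no healthy participant with a QTcF of 480 msec or more in the thorough QT study. Neither finding comes from AML patients on interacting drugs, so risk is lowered, not excluded.

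Two stronger readings are tempting. A reader might infer that the protocol leaves the dose wholly undetermined, with continuing at 50 mg and stopping equally supported. It does not: Table 10 directs resumption, and stopping rests only on the general discretion that applies to every subject. A reader might also infer from Section 5.8.1 that Table 10 overrides the escalation ban. Sections 5.8.1 and 7.1.7 only direct sites to the table; neither exempts anyone from Section 5.5.5.1.

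**Conclusion.** The point holds as a minor drafting error in a safety table. For a subject at 50 mg because of non-QTcF toxicity, with no earlier QTcF interruption, Table 10 literally gives 75 mg, 50% above the current dose, and Section 5.5.5.1 forbids it. The implied dose is 50 mg, but the table does not say so.

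This rests on reading the row as written, with no unstated condition on current dose, and on treating 50 mg as the lowest permitted level because none lower is listed. The number of subjects affected cannot be derived from the documents and is probably small, since the sequence needs two earlier reductions and then a first Grade 3 QTcF event at half the starting dose. For placebo subjects there is no drug exposure. Alpha, power and the overall survival analysis are unaffected.

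**What to change.** Amend the Table 10 row for no earlier QTcF interruption along these lines: *resume at 75 mg once daily, or at the dose at interruption if that is lower (ie, a subject already at 50 mg resumes at no more than 50 mg)*. Keep the recovery condition in that row and the existing discretion in Section 5.5.5.1 to discontinue.

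Leave every other Table 10 step unchanged. The Amendment 5 entry in the Document History says the table was updated to align with the US package insert. Whether a subject already at 75 mg, or at 50 mg after one earlier QTcF interruption, should step down further is a clinical choice outside this point.

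The cost is one line in the next amendment. The cap restates a rule already in force, so it changes no sample size, analysis or data collection.

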**Table 11. Dose Modifications for glasdegib/placebo in Case of Drug Class Related AEs**

Muscle Spasms or Myalgia	Grade 1	Grade 2	Grade 3
Glasdegib/ Placebo	
Continue at same dose level.
 
Administer oral rehydration solutions containing electrolytes.a
 
Consider other appropriate interventions (eg, anti-spasmodics) as per institutional guidelines.
 
Evaluate levels of: CK, Vit B6, Vit D, ferritin, transferin and electrolytes (Na, K, Mg, Ca and P).b
 
If CK is elevated, evaluate urine and serum myoglobin, CK isoenzymes, and plasma creatinine.
	
Continue at same dose level.
 
Administer oral re-hydration salts containing electrolytes.a
 
Consider other appropriate interventions (eg, anti-spasmodics) as per institutional guidelines.
 
Evaluate levels of: CK, Vit B6, Vit D, ferritin, transferin and electrolytes (Na, K, Mg, Ca and P).b
 
If CK is elevated, evaluate urine and serum myoglobin, CK isoenzymes, and plasma creatinine.
 
If event persists, hold dose until resolution to Grade ≤1.
 
Upon resolution, restart at prior dose, or for prolonged muscle spasms, consider reducing dose by one dose level.
	
Hold dose.
 
Administer oral re-hydration salts containing electrolytes.a
 
Consider other appropriate interventions (eg, anti-spasmodics) as per institutional guidelines.
 
Evaluate levels of: CK, Vit B6, Vit D, ferritin, transferin and electrolytes (Na, K, Mg, Ca and P).b
 
If CK is elevated, evaluate urine and serum myoglobin, CK isoenzymes, and plasma creatinine.
 
Upon resolution to Grade ≤1, restart study treatment at next lower dose level.
 
If the event does not resolve within 3 weeks to Grade ≤1, at the discretion of the Investigator the dose may be restarted at the next lower dose level or the subject may be permanently discontinued from study treatment.


Abbreviations: CK creatinine kinase; Vit vitamin; Na sodium; K potassium; Mg magnesium; Ca calcium; P phosphorous.
 
a. Electrolyte replacement drinks should include Na, K, Mg, Ca and P. Consideration should be given to ensuring adequate hydration prior to bedtime, and whenever fluid intake is decreased for a prolonged duration.
 
b. Labs may be drawn as unscheduled assessments between protocol visits.
 
In the event of alopecia or dysgeusia, investigator discretion should be applied with respect to dose interruption and/or dose reduction of glasdegib/placebo as preliminary analysis of available clinical data suggests that these events are not dose dependent.
			

### **5.5.5.3. Intensive Chemotherapy and Non-Intensive Chemotherapy**

For subjects in the Intensive Chemotherapy study, Central supply (provided by Pfizer) or locally obtained commercial supplies of daunorubicin and cytarabine will be used. Refer to the local package insert (or SPC) or Investigational Product Manual for dose modification criteria.

For subjects in the Non-Intensive Chemotherapy study, Central supply (provided by Pfizer) or commercially available azacitidine will be used ([Section 5.4.1.2](#)). Refer to the local package insert (or SPC) or Investigational Product Manual for dose modification criteria.

